In summary, the current project will (1) develop a theory-based, user-friendly, and efficient set of targeted cessation materials to facilitate extinction during pre-quit VLNC smoking, (2) establish the feasibility of recruitment and measurement strategies to be used in the RCT, (3) determine whether immediate vs. gradual pre-quit nicotine tapering in combination with the targeted behavioral intervention has beneficial effects (on cessation-related and intermediate outcomes) for eventual comparison with validated cessation methods (e.g, NRT), and (4) examine several potential moderators and mediators of treatment efficacy.

C. INNOVATION

There are several innovative features to this proposed research. Few studies have evaluated VLNC cigarettes as a tool for smoking cessation, and none have used a formative process to develop specific adjunct materials to maximize efficacy. The current project will be the first to develop a set of theory-driven self-help materials to support the use of VLNC cigarettes during the pre-quit period. A combined qualitative and quantitative approach for developing this targeted intervention, as well as evaluating the feasibility of the strategy and methods for its evaluation in the subsequent RCT, is novel. Furthermore, most prior evaluations of VLNC cigarettes have been conducted on non-treatment smokers, without the intention to quit smoking. The present study will recruit treatment-seeking smokers, which places greater emphasis on determining how VLNC cigarettes affect those most likely to guit. Another innovative feature is the unique combination of baseline and outcome measures, which will provide a valuable perspective on the effects of VLNC cigarettes on indices of nicotine dependence and reinforcement, smoking behavior, and motivation to smoke among treatmentseeking smokers. In particular, the measurement of intermediate outcomes (i.e., cue reactivity, cigarette purchase task) will provide unique insights into the effects of VLNC cigarettes on smoking behavior among treatment-seeking smokers. Finally, measurement of potential moderators (e.g., smoking history, nicotine dependence, withdrawal sensitivity, guit motivation, gender) and mediators (compliance, product perception) of the effects of VLNC cigarettes on cessation-related and intermediate outcomes will guide and support optimal utilization of this novel cessation strategy in future research and clinical application.

D. APPROACH

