3) Practicality represents the broadest of the feasibility constructs. This will encompass the degree to which we are able to carry out all the elements of the planned developmental pilot study successfully and efficiently. This includes recruitment, screening, randomization, and treatment components. For these elements of the study, we will record number of attempts, duration, protocol deviations and errors, and suggestions for improvement.

Study 2. Randomized Controlled Trial (Aim 2), Intermediate Outcomes (Aim 3), and Mechanisms (Aim 4)

Study Goals and Overview. The primary goals of Study 2 are to test effects of the targeted intervention developed in Study 1 on smoking cessation (Aim 2) and intermediate outcomes (Aim 3), as well as to explore potential mechanisms that could guide future implantation of this treatment strategy (Aim 4). Approximately 300 treatment-seeking smokers will be screened using similar methods and inclusion/exclusion criteria as in Study 1. The expectation is that 80% of participants (n=208) will be eligible and randomized to one of four conditions (52 per condition) over a 3 year period. The four conditions will comprise a 2 x 2 between-subjects design, with facilitated extinction (targeted) treatment (present vs. absent) crossed with tapering schedule (immediate vs. gradual). As in Study 1, once a participant has been deemed eligible, a baseline week of smoking NNC study cigarettes will be followed by four weeks of smoking VLNC cigarettes, either through immediate or gradual reduction to the lowest level. Five weekly counseling sessions will occur (at the start of each week), and the Target Quit Date will occur one week after the fifth weekly session (+/- 3 days). On the Target Quit Date, participants will attend an additional session, including counseling as well as two tests of intermediate outcomes (cue reactivity and cigarette purchase task). Follow-up visits will occur at 2 and 6 months following the TQD (+/- 7 days). Please see Appendices on pages 33-34 for further details.

Exclusion Criteria: Study 2 exclusion criteria will match those of Study 1, with the following modifications: (a) use of smoking cessation medications will be exclusionary only for the past month and with the exception of sporadic use of NRT for non-cessation purposes, (b) use of

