Sample Size Determination. The planned sample size (n=20) for the developmental pilot study (Study 1; Aim 1) is based on considerations of practicality and usefulness. A primary focus of Study 1 will be on evaluation of feasibility (acceptability, demand, practicality) of the procedures, and determining potential improvements to incorporate into the subsequent RCT (Study 2). In the context of the goals and project timeline, the planned sample size for the developmental pilot study should provide the team with ample information to inform the RCT (Study 2). The planned sample size (n=208) for the RCT (Study 2) is based on considerations of statistical power and anticipated effects for the primary hypothesis regarding treatment outcomes (Aim 2). We assume those who receive the standard intervention (n=104) will achieve a 20% 7-day point prevalence abstinence rate at the 6-month follow-up. Based on an intent-totreat data analytic approach and a two-sided alpha = .05, the proposed sample will have .80 power to detect approximately an 18% improvement in abstinence rate among those who receive the targeted intervention. This magnitude of improvement would be clinically significant. and worthy of further refinement and application. A similar magnitude of effect would be detectable as a function of tapering schedule. No interaction effects (between intervention and tapering schedule) are predicted. Power is likely to be greater for detecting treatment effects on dichotomous cessation outcomes at the 2-month follow-up, continuous cessation outcomes at both follow-up timepoints, and intermediate (proximal) behavioral outcomes (Aim 3). Moreover, within-condition correlations as small as 0.28, and total-sample incremental R^2 as low as 0.07 (based on six predictors) would be detected, suggesting that the moderator analyses (Aim 4) would be adequately powered to detect clinically significant effects.

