Aim 4 - Exploratory Mechanisms. As a Stage II study, we will evaluate potential moderators and mediators of treatment efficacy with VLNC cigarettes, as well as intermediate outcomes. Potential moderators include demographic variables (gender, age), smoking history, nicotine dependence, withdrawal sensitivity, and initial guit motivation. For these analyses, mixed models described for Aims 2 and 3 will be repeated, with potential moderator variables entered as interaction terms. Given multiple potential moderators and outcome variables, the Benjamini-Hochberg approach will be used to control the false discovery rate (FDR; Benjamini & Hochberg, 1995). Mediation analyses will examine smoking reinforcement, compliance with prequit VLNC smoking rate and other recommendations (e.g., smoking in multiple cue contexts), nicotine withdrawal during VLNC transition and post-TQD, and product perceptions (e.g., ratings of taste, likeability, and acceptability) as potential mediators of treatment effects on smoking cessation and intermediate outcomes. For these analyses, we will first apply a traditional causal steps approach (e.g., Baron & Kenny, 1986), using a series of regression equations to infer an indirect effect of the potential mediator. Regardless of the outcome from that approach, we will also utilize a bootstrapping approach in order to provide a more powerful and interpretable test of the indirect effects of potential mediators (Preacher & Hayes, 2008).

Study/Design Considerations

Biomarkers. We are not proposing extensive biomarker analyses in the present application. We considered this to be redundant with comprehensive safety analyses already undertaken with these and similar products, leading to the overall conclusion that they are no less safe than commercial cigarettes (already being used by all participants), and that they are not associated with sustained compensatory smoking that might increase toxicant exposure. By focusing on

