Regulatory documents and case report forms will be reviewed routinely by the MCC Clinical Research Monitoring Core for accuracy, completeness and source verification of data entry, validation of appropriate informed consent process, adherence to study procedures, and reporting of SAEs and protocol deviations according to MCC Monitoring Policies.

Trained study staff will monitor participants closely throughout each treatment and lab session, and either the study PI or a Co-Investigator will be at the study site to address any concerns that arise. Research staff will report Adverse Events (AE) to the PI and capture the AE data in Oncore, Moffitt's Clinical Trials Database. Serious Adverse Events (using the FDA definition of SAEs) will be reported according to the requirements of the FDA, Moffitt's Protocol Monitoring Committee, and the IRB. Any IRB actions in relation to this protocol will also be reported to NIH.

F. INCLUSION OF WOMEN AND MINORITIES

Inclusion of Women

We plan to recruit equal numbers of males and females. Gender will be examined as a potential moderator in predicting cessation or intermediate outcomes, given that men and women may be differentially reactive to the presence of nicotine during their cessation attempts. We will also be interested in determining if there are gender differences in feasibility-related outcomes (e.g., recruitment, retention, acceptances, satisfaction, and compliance).

Inclusion of Minorities

In terms of minority participation, the two largest counties in the Tampa Bay Area – Hillsborough and Pinellas – will serve as the recruitment base for the proposed research. Based on the 2010 U.S. Census, there are over 2.1 million residents in these counties, with the following racial distributions in Hillsborough and Pinellas, respectively 71.3% and 82.1% White, 16.7% and 10.3% African American, 3.4% and 3.0% Asian, with less than 1% from any other single racial group. Hispanics represent 24.9% and 8.0% of the population in Hillsborough and Pinellas, respectively. We expect our sample to closely reflect this racial and ethnic distribution, as it has in our recent studies.

LITERATURE CITED

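### The plan calls the Aim 4 moderator analyses adequately powered on the strength of two figures that are not the planned moderator-by-treatment interaction test, and it gives no power for that test

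*Combined protocol and SAP*

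**What the plan says.** The last sentence of Sample Size Determination (Statistical Considerations) states that "within-condition correlations as small as 0.28, and total-sample incremental R^2 as low as 0.07 (based on six predictors) would be detected", and presents this as "suggesting that the moderator analyses (Aim 4) would be adequately powered to detect clinically significant effects". The same paragraph sizes the trial on the primary hypothesis: 104 per intervention level, 20% abstinence on standard treatment at 6 months, two-sided alpha .05, and .80 power for a gain of about 18 points. Of that gain it says: "This magnitude of improvement would be clinically significant".

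The moderator test itself is defined under Aim 4 - Exploratory Mechanisms. The Aim 2 and Aim 3 models are repeated "with potential moderator variables entered as interaction terms". For abstinence, the Aim 2 model is a GEE with a logistic function. Six candidate moderators are named (gender, age, smoking history, dependence, withdrawal sensitivity, quit motivation), and "the Benjamini-Hochberg approach will be used to control the false discovery rate". Inclusion of Women adds: "We plan to recruit equal numbers of males and females. Gender will be examined as a potential moderator". The Innovation section says that measuring moderators and mediators "will guide and support optimal utilization of this novel cessation strategy in future research and clinical application".

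**The concern.** A moderator analysis asks whether the treatment effect differs across levels of a variable. The two quantities offered as evidence of power answer other questions.

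- A within-condition correlation shows that a variable predicts outcome inside one arm. Moderation is the difference between two such relations, which has a larger standard error.
- An incremental R^2 from six predictors is a joint 6-df test on a continuous scale. Aim 4 describes no joint test, and the primary outcome is binary.

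The adequacy conclusion therefore does not follow from its premises, whatever effect size one has in mind. False discovery rate control, which lowers power further, is not counted either.

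What is at stake is interpretation. With the sentence in the plan, a non-significant gender or dependence interaction could be presented as an adequately powered null. A significant one could be taken near face value, although an estimate has to be large to reach significance in a sample of this size.

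**Working it through.** **Inputs.** From Sample Size Determination: two-sided alpha .05; 104 per intervention level; 20% on standard and 38% on targeted treatment; r = 0.28; R^2 = 0.07 with six predictors; N = 208. From Inclusion of Women: equal numbers of men and women, hence 52 per intervention-by-gender cell. From Aim 4: six named moderators. Assumed: 20% abstinence on standard treatment in both subgroups, and 18 points as the size of modification.

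**1. The plan's own figures reproduce.**
- Main effect, 20% vs 38%, 104 per level: power .82 (pooled z) or .78 (Fisher exact).
- Correlation: atanh(.28) × √(104 − 3) = .2877 × 10.05 = 2.89, power .82. With n = 52 it would be .52, so *condition* here must mean an intervention level of 104, not one of the four randomized cells.
- R^2 = .07, 6 df, N = 208: noncentrality 208 × .07/.93 = 15.7, power .85.

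**2. The plan's r, asked as a moderation question.** Let the correlation be .28 at one intervention level and 0 at the other.
- z = .2877 / √(1/101 + 1/101) = .2877 / .1407 = 2.04.
- Power is .53 at alpha .05, and .28 at .05/6, the first Benjamini-Hochberg step when one of six moderators is real.

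**3. Abstinence with a balanced binary moderator, 52 per cell.** Take a targeted effect of 9 points in one subgroup (20% to 29%) and 27 in the other (20% to 47%): mean 18, difference 18.

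*Risk-difference scale.*
- SE = √[(.20×.80 + .29×.71 + .20×.80 + .47×.53)/52] = .122.
- z = .18/.122 = 1.47, power .31.

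*Logit scale, the scale of the planned model.*
- The log ratio of odds ratios is .775 (ratio 2.17).
- SE = √[(1/52) × (1/.16 + 1/.2059 + 1/.16 + 1/.2491)] = .641.
- z = 1.21, power .23.

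At .05/6 the two powers are about .12 and .08.

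**4. Other patterns, 18-point modification, 52 per cell.**

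| Subgroup 1; subgroup 2 | Power, risk difference | Power, logit |
|---|---|---|
| 20→20%; 20→38% | .34 | .27 |
| 20→38%; 20→56% | .31 | .21 |
| 15→24%; 25→52% | .32 | .15 |
| 25→34%; 15→42% | .31 | .33 |
| 20→11%; 20→29% | .38 | .38 |

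If only the 138 participants expected at 6 months (note to the Project Timeline table) were analysed, 34.5 per cell, the pattern in step 3 gives .22 and .17. A 9-point modification with 52 per cell gives .11 and .09.

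**5. What would be detectable.** Holding the mean effect at 18 points, .80 power needs a modification of about 41 points in the logistic model, or about 33 on the risk-difference scale. To detect 18 points with .80 power would take about 1,116 participants on the logit scale, or about 751 on the risk-difference scale.

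**6. The plan's R^2 on the same footing.** For one balanced binary interaction of size d, R^2 = (d²/16)/(.29 × .71). So d = .18 gives about .01, and R^2 = .07 corresponds to d of about .48, or 48 points.

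**The case against.** The strongest reply is that the plan already treats Aim 4 as exploratory. Specific Aim 4 and the section heading both say so, false discovery rate control is specified, the sample size rests on Aim 2, and Future Directions leaves better-powered replication of moderators and mediators to later research. That is fair and limits the weight of the point. It does not withdraw the adequacy sentence, which makes a power claim that an exploratory aim does not need.

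Three further objections stand in part.

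- **The 18-point size is borrowed.** The plan calls 18 points clinically significant for the main effect and sets no target for modification. The figures are conditional on that choice and on a balanced split. No pattern tried for an 18-point modification comes near .80, and a smaller target does worse.
- **The abstinence figures do not cover every outcome.** Aim 4 also applies to continuous and repeatedly measured outcomes, where the plan expects more power. A single 1-df term with R^2 = .07 in a linear model would have power of about .98, and the detectable 1-df R^2 is about .037. A reader might infer that all Aim 4 tests have power of .2 to .3; the documents do not support that.
- **Use of a null result is not stated.** Nothing in the plan says that a non-significant interaction will be read as no moderation. That is a risk the sentence opens, not a stated intention.

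A reader might also infer that r = 0.28 is a miscalculation because only 52 are randomized to each condition. It is not: the same paragraph works with 104 per intervention level, at which .28 is detectable. Nor does the point reach the intervention-by-taper interaction, for which the plan makes no power claim.

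**Conclusion.** The concern holds in a limited form. The statement that the moderator analyses are adequately powered is unsupported: it rests on prediction within an arm and on a six-predictor block increment, while the planned test is a moderator-by-treatment interaction for which no power is given.

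For abstinence, power for an 18-point modification is about .23 in the planned logistic model and .31 on the risk-difference scale, with about .15 to .38 across plausible patterns. Under the step 3 pattern, the test would miss such a modification in roughly 7 to 8 trials out of 10, before false discovery rate control. On the risk-difference scale an estimate must exceed about 1.96 × .122 = 24 points to reach p < .05, so a true 18 points that is declared significant is overstated by at least a third (24/18).

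These figures assume a 50:50 binary moderator, a single 6-month comparison and, except in the 138-participant variant, all 208 analysed. The logic of the point, and the .53 for the plan's own r, do not depend on the 18-point benchmark. The stronger conclusion, that the trial's sample size or primary analysis is deficient, does not follow.

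**What to change.** In Sample Size Determination, replace the adequacy clause with:

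> *Moderator analyses are exploratory and are not powered. For abstinence and a balanced binary moderator, .80 power in the planned logistic model requires the targeted effect to differ by about 41 percentage points between levels (about 33 on the risk-difference scale); power for an 18-point difference is about .2 to .3 before false discovery rate control.*

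If r = 0.28 is kept, state that it is for 104 per intervention level and concerns prediction within an arm.

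Under Aim 4, add that each interaction is reported as an estimate with a 95% CI, and that a non-significant interaction is not read as evidence of no moderation.

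The cost is a few sentences. Sample size, visits and models do not change. The one consequence is that the moderator results must be presented as hypothesis-generating, which is close to how the plan already labels them.

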Aim 2 – Treatment Efficacy. Analyses will focus on the incremental efficacy of targeted intervention, in combination with two tapering regimens for transition to VLNC cigarettes during the pre-quit period, on clinical outcomes. The primary outcome variable will be 7-day point prevalence abstinence at each follow-up assessment, with secondary outcomes that include continuous abstinence since the TQD, days to first smoking lapse, and smoking reduction relative to baseline (see Ditre et al., 2012). Mixed modeling will be used to test hypotheses related to these treatment outcome effects. The advantages of these models is that they allow for data that is missing at random and are more flexible than repeated measures ANOVA in terms of the underlying variance/covariance matrix (Littell et al., 2006). For point prevalence and continuous abstinence variables, a 2 (intervention: targeted vs. standard) x 2 (transition: immediate vs. gradual) analysis will be used to test the independent and combined effects of each treatment factor on these cessation outcomes, using Generalized Estimating Equations (GEE) with a logistic function for dichotomous outcomes.

Aim 3 - Intermediate Outcomes. Aim 3 includes testing effects of the intervention on intermediate (proximal) outcomes during the cue reactivity and cigarette purchase tasks. Findings may support decisions regarding which tapering schedule is optimal for further testing and/or dissemination, and may provide insight as to the mechanisms that underlie positive cessation outcomes. As in Aim 2, mixed modeling will be used to independently test the effects of targeted intervention and tapering schedule on outcomes from these two paradigms. Indices of smoking-related behavior from each paradigm (cue reactivity: self-reported craving in response to smoking cues; cigarette purchase task: hypothetical cigarette consumption across a range of prices) will be examined through separate models that test effects of intervention (targeted vs. standard) and tapering schedule (immediate vs. gradual) on these outcomes. In addition, Generalized Estimating Equations (GEE) models with a logistic function will be used to examine intervention effects on dichotomous outcomes.

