intervention development and testing, we hope to reduce participant burden and expense, and more closely represent a real-world application of this potential treatment method. Nonetheless, we will carefully track smoking rate (all sessions), carbon monoxide (all sessions), and urinary cotinine (baseline and follow-up sessions, as applicable) levels, and use medically established cut-offs (established by the Center for the Evaluation of Nicotine in Cigarettes; U54, MPI's: [name]/[name]) to guide decisions regarding early termination.

Project Timeline

Study 1 is expected to comprise the first 1.5 years of funding (see details above). Study 2 will be completed over the remaining 3.5 years (Table 2).

| Task | | Year 1 | | Year 2 | | Year 3 | | Year 4 | | ar 5 |
|---------------------------------|---|--------|---|--------|---|--------|---|--------|---|------|
| Study 1 | X | X | X | | | | | | | |
| Study 2 - Recruitment | | | | X | X | X | X | X | X | |
| Study 2 - Follow-up Assessments | | | | | X | X | X | X | X | X |

Table 2. Project Timeline

Note: Expected number of sessions for Study 2 is 208 screening/baseline, 198 week 1 pre-quit, 188 week 2 pre-quit, 178 week 3 pre-quit, 168 week 4 pre-quit, 158 target quit date, 148 2-month follow-up and 138 6-month follow-up which equals 1384 sessions in 42 months. This is approximately 33 sessions/month.

Participant Compensation (cash or gift card):

- Participants will receive \$25 for completing the baseline session. If an additional visit is needed (e.g., to rescreen for alcohol or drugs, or due to a pending LMP/PI/Co-I eligibility determination), a \$20 payment will be provided for completing the additional visit.
- Following the screening visit, they will receive \$25 for completing each weekly session (including Target Quit Date for Study 2), and an additional \$10 for each session in which they arrive on time, without rescheduling, and bring the treatment booklet with tracking exercises completed.
- COVID-19 considerations: The \$10 weekly session bonus will apply to timeliness and preparedness regarding the in-person assessments, as well as the timely completion of telephone assessments.
- -
- For Study 1 they will receive \$35 for completing a follow-up session after the TQD. This session will include brief counseling, as well as obtaining feedback using a standardized form and a debriefing interview.

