The proposed project will develop and pilot test a targeted smoking cessation intervention strategy based on VLNC cigarette smoking during the pre-quit period, and then conduct an initial RCT to test this cessation method in the context of two distinct nicotine tapering regimens. Future work will likely entail improvements in the targeted treatment materials based on the experience from this project, as well as a determination as to which tapering schedule (immediate vs. gradual) is optimal in terms of acceptability, practicality and effects on cessationrelated and intermediate outcomes. The optimal intervention from this project could then be compared to existing validated treatment strategies, such as NRT. Subsequent research may also incorporate newer mobile technologies to more precisely track adherence during the prequit period and cessation in the post-quit period. In addition, the current proposal will begin to explore several potential moderators and mediators of treatment efficacy, whereas later research may include replication testing (with increased power) to further refine an understanding of how (and for whom) this cessation approach may be optimal. Future research will also continue to examine the optimal amount, type, and duration of pre-quit VLNC smoking for successful cessation outcomes, as well as how VLNC cessation strategies may be used in in the context of potential FDA regulation to lower nicotine standards in cigarettes at a national level. Finally, successful outcomes in the current project will lead to work intended to broadly disseminate a cessation strategy based on VLNC cigarettes.

E. PROTECTION OF HUMAN SUBJECTS

Risk to the Subjects

Human Subjects Involvement and Characteristics: Cigarette smokers (n=228) who are interested in quitting will be recruited for a developmental pilot study (Study 1; n=20) or a randomized controlled trial (RCT; Study 2; n=208). Males and females will be recruited equally, and ethnic/racial distributions are expected to closely represent the Tampa Bay area. Participants who pass an initial telephone or web-based screening will be invited to attend a

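### Abstinence is primary at both 2 and 6 months, but the trial is sized on one 6-month comparison, and nothing makes that comparison the sole primary test with overall error of 5%

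*Combined protocol and SAP*

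**What the plan says.** All references are to the combined protocol and SAP.

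- **Aim 2 – Treatment Efficacy** defines the endpoint: "The primary outcome variable will be 7-day point prevalence abstinence at each follow-up assessment". Study Goals and Overview (Study 2) and Follow-up Assessments both place the follow-ups at 2 and 6 months after the target quit date.
- The same Aim 2 paragraph describes the model by the treatment factors: "a 2 (intervention: targeted vs. standard) x 2 (transition: immediate vs. gradual) analysis will be used to test" their independent and combined effects, by logistic GEE. It states no visit term, factor-by-visit term, 6-month contrast or rule for declaring success.
- **Sample Size Determination** ties N=208 to a single primary hypothesis. It assumes that the standard arm (n=104) "will achieve a 20% 7-day point prevalence abstinence rate at the 6-month follow-up", and claims .80 power at two-sided .05 for an improvement of about 18 points with the targeted intervention. The 2-month visit appears only later, in a remark with no rate or alpha attached: "Power is likely to be greater for detecting treatment effects on dichotomous cessation outcomes at the 2-month follow-up".
- **Aim 4 – Exploratory Mechanisms** contains the only multiplicity rule: "Given multiple potential moderators and outcome variables, the Benjamini-Hochberg approach will be used to control the false discovery rate". It is written for the moderator analyses, not for Aim 2.

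**The concern.** The endpoint definition and the sample size describe different primary tests. One section gives abstinence primary status at two visits. The other spends the whole .05 on one visit. Nothing between them says whether the visits are tested separately, pooled into one effect, or modelled jointly with the 6-month effect extracted.

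These choices answer different questions. With separate tests and no rule for discordant results, a finding at 2 months alone could be reported as a primary success of a trial sized for 6-month abstinence. With pooling, a short-lived effect could carry the averaged result, or a 6-month effect that was absent at 2 months could be diluted. The choice would be made after the data are in.

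The stakes are moderate. This is an early-stage trial, but Future Directions looks ahead from its results: "The optimal intervention from this project could then be compared to existing validated treatment strategies, such as NRT".

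**Working it through.** **Inputs from the plan.** 104 per intervention level (208 in a 2 x 2 with 52 per cell); standard-arm abstinence 20% at 6 months; improvement of about 18 points; two-sided alpha .05; stated power .80. The plan gives no between-visit correlation and no 2-month rate, so those are assumed below.

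**1. Reproduce the sizing.** Two-proportion z-test, pooled variance under the null:

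power = Φ[(d − z·SE0) / SE1], with SE0 = √(2·p̄(1−p̄)/n) and SE1 = √([p1(1−p1) + p2(1−p2)]/n).

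For 20% versus 38%, n = 104 and p̄ = .29:
- SE0 = √(2 × .29 × .71 / 104) = .0629
- SE1 = √((.16 + .2356) / 104) = .0617
- power = Φ[(.18 − 1.96 × .0629) / .0617] = Φ(.92) = .82

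Power reaches .80 at a difference of 17.5 points, which rounds to the stated 18. The sizing is sound for one 6-month test at .05.

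**2. Visits tested separately, each at .05.** The 6-month test keeps its own 5% error and its power of .82. If significance at *either* visit counts as success, the error for the intervention factor under no effect is

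1 − P(|Z2| < 1.96 and |Z6| < 1.96), with (Z2, Z6) bivariate normal with correlation ρ.

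| assumed ρ | at least one false positive | 2-month test only |
|---|---|---|
| .4 | .0932 | .0432 |
| .5 | .0907 | .0407 |
| .6 | .0875 | .0375 |
| .8 | .0781 | .0281 |

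The last column is the middle column minus .05. With independent tests the figure would be 1 − .95² = .0975.

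**3. Visits pooled into one effect.** Logistic GEE with visit and intervention, independence working correlation, robust standard errors, all 104 per group classified, 40,000 simulated trials at each of ρ = .4/.5/.6:
- *No effect at either visit:* rejection .050/.051/.049, so type I error holds.
- *20% versus 38% at both visits:* power .933/.914/.893. Pooling does no harm here.
- *20% versus 38% at 2 months, 20% versus 20% at 6 months:* significant in .443/.420/.392 of trials, median odds ratio about 1.65. The true 6-month odds ratio is 1.00, and the sized one is (.38/.62)/(.20/.80) = 2.45. As a rough check, the visit-averaged rates are 20% and (38 + 20)/2 = 29%, giving (.29/.71)/(.20/.80) = 1.63.

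The reverse pattern, by a normal approximation to the visit-averaged risk difference: 30% versus 30% at 2 months and 20% versus 38% at 6 months. The average difference is (0 + .18)/2 = .09. At ρ = .5, SE0 = .0548 and SE1 = .0542, so power = Φ[(.09 − 1.96 × .0548)/.0542] = Φ(−.32) = .37. The range is .42 to .34 for ρ = .3 to .7, against .82 for the sized 6-month test.

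**4. Both visits kept primary at .025 each.** With z = 2.241, 6-month power = Φ[(.18 − 2.241 × .0629)/.0617] = Φ(.63) = .74. Restoring .80 at 18 points needs 120 per group, 240 in total.

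**The case against.** A reader might infer that under no reading is the 6-month comparison tested at 5%. The documents do not support that. Under separate testing it is run at exactly .05 with power .82. A GEE with a factor-by-visit term and a 6-month contrast, which would deliver the sized test directly, is also compatible with the Aim 2 wording. It is neither stated nor excluded.

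The error inflation also depends on an either-visit success rule that the plan does not contain. If both visits had to be significant, error would not exceed 5%, at the price of joint power of about .65–.74 (assuming an 18-point effect at both visits, 2-month control rates of 20–30% and correlation .3–.7). Sample Size Determination, with its one primary hypothesis at 6 months, can be read as settling the matter: one variable, measured twice, with the sized hypothesis at 6 months. The pooled scenarios are constructed extremes, and the 39–44% is power for a real averaged effect, not a false-positive rate. Finally, Future Directions does not tie the next step to a primary p-value.

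Most of this stands, and it limits the claim. It does not remove the conflict. The Aim 2 text gives primary status to each follow-up, no section names 6 months as the primary timepoint, and no success rule is written. The 6-month reading is plausible, but the plan should say so before analysis.

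**Conclusion.** The concern holds as a conflict between the endpoint definition and the sizing, left open by the model description: the plan does not make the sized 6-month comparison the sole primary test with overall error of 5%. The sizing itself is not in error.

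Its size depends on the reading:
- *Separate tests with either-visit success:* overall error of about 7.8–9.3% for the intervention factor, for assumed correlations of .8 to .4.
- *Pooled effect:* error is 5%, but what is tested is a 2- and 6-month average. It can differ from the 6-month effect in either direction when the effect changes over time, and it is harmless when the effect is equal at both visits.

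The .82 assumes that all 208 participants are classified at 6 months, as the intent-to-treat wording implies. That condition applies equally to the plan as it stands. This should be corrected, with stakes limited by the trial's early stage.

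**What to change.** In Aim 2 – Treatment Efficacy:
- Name 7-day point prevalence abstinence at 6 months as the single primary timepoint.
- Make the 2-month result a named secondary.
- State that the GEE includes visit and factor-by-visit terms.
- Take the 6-month targeted-versus-standard contrast from that model, tested at two-sided .05.

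The status of the tapering comparison should be left to the sponsor. Specific Aim 2 names it alongside the intervention, so demoting it would change an objective rather than clarify one.

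The cost is analysis-plan wording. N=208 and the stated power do not change. The downside is that the 2-month result can no longer be called primary. Keeping both visits primary at .025 each is possible, but it lowers 6-month power to .74 unless the sample rises to about 240.
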